### **Inspiratory scan**

The patient will be asked to take a full inspiration and breath hold before a scan is taken. The scan is expected to take a few seconds. The manouvere will be practiced 3-4 times before the actual scan to support good inspiratory scan.

### **Expiratory scan**

Similar to the inspiratory scan the patient will be asked to exhale and hold the breath. The expiratory scan uses a low radiation dose protocol and is expected to take few seconds.

## 6.3.2 Lung function measurements by body plethysmography

Lung volumes, IC (L), TLC (L), FRC (L), RV (L) and SGaw (sec x kPa) will be measured at Visits 2 and 6 using body plethysmography. Measurements should be performed before pre-bronchodilator spirometry measurements.

Body plethysmography measurements should be performed according to ERS guidelines (Wanger J et al 2005).

All results will be recorded in the eCRF and the detailed instructions are given in a separate manual of procedures.

## Equipment

Body plethysmography parameters will be measured using the body plethysmograph available at the study site.

## Calibration

Calibration of the body plethysmograph should be done continuously during the study according to ERS guidelines (Wanger J et al 2005).

Clinical Study Protocol Drug Substance AZD9668 Study Code D0520C00014 Edition Number 1 Date

### **Measurements/Conditions**

After the patient enters the body plethysmograph, the measurements will start when the box pressure becomes stable. The patient will wear a nose clip while breathing through the mouthpiece. At the end of a normal expiration, the airways will be closed by the shutter for 2-3 seconds. During this time the rate of airflow and the mouth- and plethysmograph pressures will be recorded during gentle panting against the shutter. FRC will be estimated. Immediately after releasing the shutter, the patient will be instructed to perform a maximal expiration to RV followed by a maximal slow inspiration to obtain IC and TLC. This manoeuvre will be then repeated twice. Means of the 2 highest measurements will be recorded. SGaw will be obtained at flow rate of 0.5 L/sec of inspiratory and expiratory flows at a respiratory rate of 0.5 Hz. Means of three measurements will be recorded.

## 6.3.3 Diffusion capacity of the lung for carbon monoxide (DLCO)

Diffusion capacity (mmol/min/kPa) will be measured before pre-bronchodilator spirometry measurements at Visits 2 and 6.

Diffusion capacity will be measured based on the single breath diffusion capacity manoeuvre according to ERS guidelines (Macintyre N et al 2005).

## Measurements/conditions

The patient will rest for at least 10 minutes. The measurement will be conducted in sitting position. The mean of at least 2 measurements will be recorded.

The patient inhales a known volume of test gas (10% helium, 0.3% carbon monoxide, 21% oxygen, and the remainder nitrogen), and holds his or her breath for 10 seconds. The patient exhales to wash out a conservative overestimate of mechanical and anatomic dead space. Hemoglobin concentration is important for assessing  $DL_{CO}$ , and the  $DL_{CO}$  assessment has to be corrected for the patient's hemoglobin level according to normal routine at the site.

## 6.3.4 Lung function measurements by spirometry

Pulmonary function,  $FEV_1$  (L), FVC (L) and SVC (L), will be measured by spirometry (preand post-bronchdilator) and collected in the eCRF at Visits 1b to 6 as defined in Table 2. Measurements at Visits 2 to 6 should be performed pre-dose of AZD9668.

## Equipment

Spirometers used in this study should meet the American Thoracic Society (ATS) and European Respiratory Society (ERS) recommendations (Miller MR et al 2005) and the same spirometer should be used for each patient throughout the study. The monitor is responsible for checking that the spirometer in use meets these recommendations.

The spirometer should be serviced once a year or according to the manufacturer's instruction at an authorised facility. All service measures and repairs must be documented.

A nose-clip should be used for the manoeuvre. Mouthpieces of the same dimension and shape should be used throughout the study.

Spirometry data should be given at BTPS (body temperature, barometric pressure and saturated with water vapour), using a calibrated spirometer.

### Calibration

Calibration should be in accordance with the specification for the trademark.

If nothing else is specified, calibration should be performed every day when a patient visits the clinic. Instead of using a 3 L syringe, a 1 L syringe can be used 3 times. The accuracy of the calibration must be within  $\pm 3\%$  of the reading or  $\pm 0.05$  L, whichever is greater. All calibration reports should be signed, dated and filed in the ISF along with a signed and dated copy (if the calibration reports are not on archive proof paper). If a calibration report can not be printed, the results should be documented in writing in the ISF.

### **Measurements/Conditions**

Spirometry should be performed according to the ATS/ERS considerations for lung function testing guideline (Miller MR et al 2005, Miller MR et al 2005). It is of great importance that all spirometry measurements take place  $\pm 1$  hour relative to the time of the Visit 2 measurement (baseline) and between 7am and 11am.

Before spirometry testing the following restrictions apply:

- Patients taking tiotropium from Visit 1a should not take their morning dose at home before Visit 1b
- Patients should not take tiotropium at home in the morning of Visit 2
- Patients should not take investigational product (AZD9668 or placebo) or tiotropium at home in the morning of Visits 3 to 6
- Patients should refrain from taking their reliever medication, if possible, within 6 hours prior to the measurements at the clinic
- No alcohol within 4 hours
- No vigorous exercise within 2 hours

- No large meals within 2 hours
- No prohibited medication as listed in Section 5.6.3.1.

The medications will be taken in clinic after completing spirometry (post bronchodilator) and other pre-dose clinical assessments.

Rescheduling the patient should be considered if less than 6 hours have passed since intake of reliever medication.

Each patient should preferably use the same spirometer during the entire study period. Preferably, the same study personnel should test the patient's lung function throughout the study to reach optimal performance and to enhance reproducibility. The patient should rest at least 15 minutes prior to the test. At repeated measurements, eg, to assess best of 3, a short pause (1 min.) between measurements is recommended.

The measurements are to be made with the patient seated in an upright position (preferably) or, if not comfortable, in standing position. The same position should be used during the entire study. The head must not be tilted during measurements. During the breathing manoeuvres, the thorax should be able to move freely; hence tight clothing should be loosened.

The spirometry measurements should always start with slow manoeuvres (SVC) and will be followed by forced manoeuvres (FVC, FEV1). Between manoeuvres, the patient will be allowed to take a rest by breathing freely for about 1-2 minutes.

### **Pre-bronchodilator SVC**

#### Slow manoeuvre

If the patient is not familiar with the assessment it is recommended to arrange a practise session, preferably done at the enrolment visit (1a) outside the ordinary lung function assessment schedule.

Before the actual measurement starts for obtaining SVC, the patient should have taken 3-5 normal breaths with the spirometer mouthpiece in place. The patient will then be prompted that after the next normal breath out, breath in until the lungs are full and then try to give an extra effort to fill up even more. They will be asked to do this fairly quickly so as not to interrupt breathing for very long. The manoeuvre will end with a normal (slow and even), unforced exhalation.

The SVC manoeuvre may be considered either as an inspiratory vital capacity (VC), where the patient inhales completely from a position of full expiration, or as an expiratory VC, where the patient exhales completely from a position of full inspiration.

The patient should be encouraged throughout the manoeuvres. For a technically satisfactory manoeuvre, it must be checked that none of the following occurs; coughing, leak or obstruction of mouthpiece (by eg, tongue or teeth).

For SVC the largest value from the acceptable manoeuvres should be reported.

A minimum of 3 technically satisfactory manoeuvres should be obtained with a maximum of 4 attempts, and with a difference in SVC between the highest and second highest of <150 mL. If less than 3 are achieved, the highest of the acceptable attempts will be used, and noted on the print-out.

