#### Post-bronchodilator assessments

After the slow and forced pre-bronchodilator manoeuvres the patient should take 4 inhalations of salbutamol pMDI 100  $\mu$ g/actuation via spacer, wait for 15 - 30 minutes and repeat the slow and forced spirometry manoeuvres as described above for pre-bronchodilator SVC, FVC and FEV1.

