### Secondary variable: Air trapping

Air trapping index provides an estimate of the air trapping in the entire lung based on CT (CT ATI). CT ATI has been shown to correlate well with physiologic ATI (VC - FVC) (Lee YK et al 2008). Air trapping will be measured by applying a threshold of -856 HU on expiratory scan.

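### The coached steps for slow vital capacity (SVC) contain no full expiration, which both of the protocol's definitions of SVC require, and the protocol does not fix which definition applies

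*Protocol*

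**What the plan says.** The procedure is in protocol Section 6.3.4, under Pre-bronchodilator SVC, Slow manoeuvre. After a few tidal breaths on the mouthpiece, the instruction is: "The patient will then be prompted that after the next normal breath out, breath in until the lungs are full". The patient tries to fill up a little further, and then: "The manoeuvre will end with a normal (slow and even), unforced exhalation".

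The next paragraph defines the variable in two ways. The first is measured on the breath in: "The SVC manoeuvre may be considered either as an inspiratory vital capacity (VC), where the patient inhales completely from a position of full expiration". The second definition is offered as an equal alternative and runs in the opposite direction, from a full lung to a fully emptied one. The paragraph does not choose between them.

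The rules for accepting and reporting a value follow. An attempt is unsatisfactory if there is coughing, a leak or an obstructed mouthpiece. At least three satisfactory attempts are wanted, "with a difference in SVC between the highest and second highest of <150 mL". Then: "For SVC the largest value from the acceptable manoeuvres should be reported".

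Under Post-bronchodilator assessments, after salbutamol, the site is to "repeat the slow and forced spirometry manoeuvres as described above".

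SVC before and after bronchodilator is a secondary efficacy variable (Synopsis; Section 2.2). Under Section 11.1 the outcome is the Visit 6 value, with Visit 2 as baseline.

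**The concern.** The coached steps and the definition do not describe the same measurement. Inspiratory VC starts from full expiration and expiratory VC ends there, yet the steps ask for full expiration at neither point. A technician who follows the steps exactly could enter an inspiratory-capacity-type volume in the SVC field. One who works from the definition would enter a vital capacity.

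The variable is compared between two visits about 12 weeks apart, across approximately 15 centres with 3 to 10 patients each. If a site always takes the shorter breath, its patients contribute a different quantity under the name SVC. If the manoeuvre changes between Visit 2 and Visit 6, the change of technique appears as a change in lung function, and adjusting for the baseline value does not remove it.

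**Working it through.** No figure in the plan can be reproduced here, because the protocol states none for this point. The check compares the texts and applies the standard lung-volume identities.

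**1. Volume spanned by each description (Section 6.3.4)**

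| Description | Start | End | Span |
|---|---|---|---|
| Coached inspiration | end of a normal breath out (FRC) | lungs full (TLC) | TLC - FRC = IC |
| Inspiratory VC, as defined | full expiration (RV) | full inspiration (TLC) | TLC - RV |
| Expiratory VC, as defined | full inspiration (TLC) | full expiration (RV) | TLC - RV |

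There are two spans: IC, and VC measured in either direction. The difference is (TLC - RV) - (TLC - FRC) = FRC - RV.

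**2. Comparison with the protocol's other manoeuvres.** Where the protocol wants the lung emptied, it says so. The forced manoeuvre in Section 6.3.4 asks for a complete expiration lasting at least 6 seconds. The plethysmography text in Section 6.3.2 asks for a maximal expiration to RV. IC is a separate outcome measured by plethysmography, so the SVC steps are not meant as a second measurement of IC. The absence of a full expiration from those steps therefore looks like a drafting fault.

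**3. Whether a stated check would catch it.** The acceptability criteria do not cover completeness of exhalation. The 150 mL criterion compares attempts within one session, so attempts that all stop short in the same way agree with one another and pass. Reporting the largest acceptable value does not help if every attempt is of the shorter type.

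**4. Size.** The documents give no value for FRC - RV. Assuming 0.5 to 1.0 L:
- relative to the repeatability limit: 0.5 / 0.15 = 3.3 and 1.0 / 0.15 = 6.7;
- as an illustration only, if one patient in an arm of 25 (Section 12.3) changed manoeuvre between visits, the arm mean would move by 0.5 / 25 = 0.02 L to 1.0 / 25 = 0.04 L, that is 20 to 40 mL.

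The 150 mL limit serves here only as a yardstick for scale. It is a within-session criterion, whereas the error in question lies between sites or between visits.

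**The case against.** The strongest reply is that the coached text can be read as an expiratory VC. It never says that the inspired volume is the one recorded. The word in parentheses explains the exhalation as slow and even, and unforced contrasts it with the forced manoeuvre that follows; neither word says that the breath stops at the tidal level. If the final exhalation is carried to the end, the sequence yields a vital capacity. This stands: a reader might infer that sites are instructed to record IC, and the text does not go that far. It permits that reading without requiring it.

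There is also mitigating text. Section 6.3.4 calls for ATS/ERS guideline spirometry, asks for the same spirometer for each patient, prefers the same staff, and requires slow-manoeuvre printouts to be kept for source verification. These make a wrong or changing technique less likely. They do not remove the conflict, because the guideline's content is not in the documents, the staffing clause is only a preference, and nothing fixes the form of the SVC breath.

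Two stronger readings should not be drawn:
- **Three different volumes under one name.** By the protocol's own definitions, inspiratory and expiratory VC are the same span in opposite directions, and the documents do not say that slow values differ by direction.
- **Damage to the air-trapping analysis.** Section 11.1.1 mentions the VC - FVC difference only as published background for the CT index: "CT ATI has been shown to correlate well with physiologic ATI (VC - FVC". That difference is neither a listed outcome nor a planned comparison.

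Finally, SVC is one of many secondary variables in a feasibility study, and under randomisation and blinding inconsistent technique should mainly add noise. That limits the consequence, but it is no reason to leave conflicting instructions in place.

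**Conclusion.** The point holds as a conflict between a stated procedure and the definition of the variable that it is meant to measure. Followed literally, the steps may give a volume smaller than VC by FRC - RV, before and after bronchodilator alike, and no stated check would detect this. The form of VC is also left open across patients and visits.

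The size is uncertain. The figure of about 3 to 7 times the 150 mL limit rests on an assumed gap of 0.5 to 1.0 L, and the shift of 20 to 40 mL in an arm mean rests on an assumed single switch. How often either error would occur cannot be judged from the documents.

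The scope is SVC only. AWT-Pi10 comes from CT, eligibility uses FEV1 and FVC from the forced manoeuvre, and the sample size reasoning concerns AWT-Pi10; none of these is affected. A correction is worth making because it protects a named secondary variable at almost no cost.

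**What to change.** In Section 6.3.4, reword the slow-manoeuvre steps so that they include a complete, slow expiration consistent with the VC definition. Replace the either/or sentence with one named form, inspiratory or expiratory VC, for all patients and all visits. State that the same form applies post-bronchodilator, and carry the wording into any spirometry instructions given to sites.

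The change adds no procedure, visit or patient burden. The one small cost is that sites used to the other form of VC must switch to the named one.

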### Pre-bronchodilator FVC and FEV1

### Forced manoeuvre

The forced expiratory manoeuvre, both to make maximal inspiration and complete expiration as hard and fast as possible, is started immediately after a maximum inspiration. The expiration should last for at least 6 seconds. It is important to encourage the patient throughout the manoeuvre, which should be as hard and fast as possible. Check that none of the following has occurred; coughing during the first second, glottis closure, leak or obstruction of mouthpiece (by the tongue).

At least 3 technically satisfactory FVC manoeuvres should be performed. The difference between highest and second highest FVC should not vary by more than 5% or 0.15 L (whichever is greater) or 100 mL if FVC is  $\leq$ 1.0L. A maximum of 8 manoeuvres should be performed in attempting to meet reproducibility criteria. If the reproducibility criteria cannot be met within 8 manoeuvres, the highest FVC value should be recorded, and a comment should be entered on the print-out.

 $FEV_1$  values will be taken from the FVC curves. After examining the data from all acceptable curves the highest FVC value and the highest  $FEV_1$  value should be recorded in the eCRF, even if the 2 values do not come from the same curve.  $FEV_1$  and FVC values will be recorded with 2 decimals throughout the study.

Signed and dated copies of the 3 best printouts for the slow and forced manoeuvres respectively must be kept in the ISF for source data verification. It is acceptable to store (in the ISF) only 1 spirometry printout if the spirometer in use automatically selects and prints the best out of 3 FVC and FEV1 curves. The printouts must be signed and marked with study code, enrolment code, date and time of measurement, visit number and patient

Clinical Study Protocol Drug Substance AZD9668 Study Code D0520C00014 Edition Number 1 Date

initials and filed in the ISF along with a signed and dated copy (if the printouts are not on archive proof paper).

#### Post-bronchodilator assessments

After the slow and forced pre-bronchodilator manoeuvres the patient should take 4 inhalations of salbutamol pMDI 100  $\mu$ g/actuation via spacer, wait for 15 - 30 minutes and repeat the slow and forced spirometry manoeuvres as described above for pre-bronchodilator SVC, FVC and FEV1.

#### FEV1 predicted normal value

At Visit 1b the post-bronchodilatory  $FEV_1$  value will be used for calculation of percentage of  $FEV_1$  predicted normal (PN) value to be used for eligibility.  $FEV_1$  % of PN value will be based on the reference values from European Respiratory Society guidelines for adult patients (Quanjer PH et al 1993). PN values by gender and age are calculated using the formulas below (Table 3). A reference list with pre-calculated PN values will be provided to the study staff at the clinic by AstraZeneca.

### Table 3FEV1 predicted normal value

FEV 1 predicted normal value			
Women	FEV 1 PN	$= (3.95 \text{ x H})^{a} - (0.025 \text{ x A})^{b} - 2.60$	
Men	FEV 1 PN	= (4.30  x H) - (0.029  x A) - 2.49	

a H: standing height in metres

b A: age (year)

FEV1 expressed as percent of PN value will be calculated according to Equation 1 below.

$$FEV_1\% \text{ of PN} = \frac{FEV_1}{FEV_{1PN}} \times 100 \tag{1}$$

N.B. When determining if a patient is eligible for enrolment according to inclusion criterion # 6 (see Section 4.1), the value for  $FEV_1$  % of PN should always be taken from the reference list provided by AstraZeneca, not from the spirometer.

### Post-bronchodilator FEV1/FVC ratio at Visit 1b

This ratio is obtained by dividing highest  $FEV_1$  measurement (L) by the highest FVC measurement (L) taken from the post-bronchodilator measurements at Visit 1b, and is used for Inclusion criterion #7 (see Section 4.1).

Clinical Study Protocol Drug Substance AZD9668 Study Code D0520C00014 Edition Number 1 Date

### 6.3.5 Daily lung function measurements by patients

An electronic diary/handheld spirometer will be dispensed at Visit 1b. The patient will be carefully instructed on how to use the diary/spirometer and written information will be supplied to each patient. The patient must understand and be willing to use the device and be instructed of how and where to request help if problems occur. The principal investigator is responsible to ensure that this training is performed at Visit 1b.

### PEF

Measurements of PEF in the morning and in the evening, expressed in L/min, will be performed from the evening of Visit 1b to the morning of Visit 6. The patient will be requested to perform 3 manoeuvres twice daily (morning and evening). The measurements should be done upon rising in the morning before intake of morning dose of tiotropium and investigational product but after clearing out mucus. Patients should also refrain from taking their reliever medication prior to the morning measurements if possible. Evening measurements to be performed before bedtime. The measurements should be made while standing. The patient should use the same handheld spirometer during the entire study. Data from the PEF recordings are transferred to a database at the clinic visits.

### $\mathbf{FEV}_1$

 $FEV_1$  readings will be made from the PEF measurements. It is important that the patients follow the instructions on how to perform the measurements, to ensure that the exhalation lasts long enough to collect a correct  $FEV_1$  value.

## 6.3.6 Patient reported outcomes (PRO)

The Patient Reported Outcomes used in the study are the BCSS, EXACT and SGRQ-C. The BCSS and EXACT are, together with questions about use of reliever medication and intake of investigational product and maintenance medication, included in the eDiary and will be completed by the patient at home. The SGRQ-C will be administered as paper questionnaires to be completed by the patient at clinic visits. The PRO data collected in the eDiary are presented in Section 6.3.8.

## St. George's Respiratory Questionnaire for COPD patients (SGRQ-C)

The SGRQ-C is a modified version of the St. George's Respiratory Questionnaire, which has been developed to measure the impact of respiratory disease on health status (Jones W et al 1991). The SGRQ-C includes 40 questions in 3 domains:

- Symptoms (distress due to respiratory symptoms, 7 questions)
- Activity (disturbance of physical activity, 13 questions)

Impacts (overall impact on daily life and well-being, 20 questions).

The original SGRQ has undergone rigorous validation and has shown to have strong evaluative and discriminative measurement properties (Jones PW et al 1992). For COPD patients, SGRQ-C has been shown to have even more favourable measurement properties than the original SGRQ (Meguro M et al 2007). Translations of the SGRQ-C into local languages have been performed according to a linguistic validation process. The English version is included in Appendix E.

